Inclusion Criteria: Subjects with CF (medical record evidence of cystic fibrosis transmembrane conductance regulator mutation or sweat chloride test or nasal voltage difference, **and** 1 or more clinical findings of CF), age 12 or greater with an FEV₁ >30% predicted (within the last 14 days) and oxygen saturation \geq 90% on FiO₂ \leq 50%, admitted for an exacerbation, able to provide written informed consent or assent.

Exclusion Criteria: Pregnancy, hemoptysis more than 60 mL within the last 30 days, use of any investigational study drug within the last 30 days, initiation of hypertonic saline within the last 30 days, known intolerance to hypertonic saline, serum creatinine 2 mg/dl or more, active malignancy in the last year, on waiting list for lung transplantation, received a solid organ transplant, lack of FEV₁ data from the last 14 days and previous participation in this study.

Experimental Treatment: Aerosolized 15% xylitol, 5 ml twice a day for 2 weeks using Pari LC nebulizer with Vios compressor, (Pari Inc, Monterey, CA) . Xylitol crystals are

made as food additives by Danisco Cultor, USA. Aerosol solution is sterile, non-pyrogenic, preservative-free solution for inhalation made by UI Pharmaceuticals (Iowa City, IA).

Control Treatment: Hypertonic 7% saline (UIHC pharmacy) 4 ml twice a day for 2 weeks using the same kind of nebulizer.

Screening and Baseline Visit: On the day of admission for exacerbation, informed consent obtained in subjects whose admission spirometry (or spirometry within the last 14 days prior to admit date) shows an FEV₁ >30% predicted. Once consented, subjects will be randomized to either xylitol or saline group as per the randomization code previously generated by the statistician. Demographics, current medications use and the revised CF quality of life questionnaire (CFQ-R) will be completed. Spontaneously expectorated sputum will be collected and processed for cell count and cytokines and quantitative cultures. Blood will be collected for chemistry and liver function tests (LFT). Pregnancy test will be done in women. All medication use during hospitalization will be recorded. Treatment will begin the day after admission for an exacerbation. Results from spirometry that is routinely done twice a week for inpatients will be recorded. All spirometry testing will follow the 2005 American Thoracic Society guidelines.

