First dose pre and post spirometry: All subjects will undergo spirometry before and 20 minutes after the first study drug dose as follows.

Perform baseline spirometry and measure SpO₂. Multiply the patient's best FEV₁ by 0.80 to obtain 20% fall in FEV₁ value.

Premedicate subject with 4 puffs albuterol and wait 15-30 min.

Begin study drug nebulization.

Wait for 15-30 minutes and repeat spirometry and SpO₂.

Subject is excluded from the study if SpO₂ is <89% or FEV₁ declines by 20% or greater from baseline.

Administration: Subjects will take their routine inhaled medicines followed by chest physical therapy. All subjects will then receive 2-4 puffs of albuterol metered dose inhaler 15-30 minutes before the study drug. Finally the study drug will be inhaled. All empty, unused and partially used study drug containers will be tracked by the investigators. Subjects will be required not to use any new treatments if not medically indicated during the study period.

Day 14 follow-up: Subjects will undergo spirometry and sputum collection and answer CFQ-R questionnaire. Blood draw for LFTS and electrolytes will be done if not done for clinical reasons. If subjects are discharged prior to 14 days of xylitol use, nebulizer solutions will be sent home. They will be asked to keep a log of nebulizer use and bring back empty and unused vials on follow-up visit (Day 10-15, preferably day 14). They will undergo spirometry and sputum collection and questionnaire administration on that day. If subjects don't return on this day, they will have a phone follow-up for adverse events and compliance.

Phone follow-up: Week 1, Day 90 and Day 180 after discharge: Subjects will be contacted by phone at these time points to enquire about further pulmonary exacerbations, admissions, and other AEs.

In the event of bronchospasm: Subjects will alert the nurses or study team members. Nebulized bronchodilators will be immediately administered. Once symptoms resolve, they will undergo spirometry using a portable handheld spirometer by a trained user. If the subjects dropped FEV₁ by 20% or greater from their baseline, they will not receive further study drug. However, they will remain in the study for completion of data collection.

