However, if a subject consents to future use and some of their specimens have already been used for research purposes, the information from that research may still be used.

Statistical analysis: We plan to enroll a total of 60 subjects for this study. These subjects will be randomly assigned to the treatment (xylitol) and control (saline) groups, with a goal of 30 subjects in each group. Since this is a pilot safety study, it has been primarily powered to detect common adverse events. Assuming that the likelihood of a subject experiencing an adverse event is no less than 5%, a sample size of 30 subjects ensures 80% power towards event detection [16]. (In other words, with a group sample size of 30, the probability of observing at least one adverse event in the group is at least 80%.)

Study Performance

Accrual will be assessed on a monthly basis. We will examine the number of screened subjects, those meeting eligibility criteria, the number of persons consenting to participate and the number of randomized. The rate of accrual will be tracked versus the expected number to achieve the target of 60 participants randomized.

We will also track the completion number and proportion by time. The number of study terminations and reason for termination will be measured. The subject will undergo a spirometry and if the FEV₁ has declined by 20%, the subject will be terminated from the study.

Baseline

The composition of the study sample will be described in aggregate. Comparison of randomized participants of baseline characteristics will be analyzed using 2 sample t-test,

Wilcoxon rank sum test, and analysis of variance (ANOVA) as indicated by the type and characteristics of the variable.

Outcomes

To assess the adequacy of these group sample sizes for testing a trend in efficacy, we consider the outcome of log CFU. We assume an average density of colonization of 6.5 log CFU with a SD of 1.5 log CFU among CF subjects. To detect a reduction of 1.5 log CFU in the xylitol group with 80% power, the required sample size is 17 subjects per group. (This computation is based on a two-sided, two-sample t-test conducted at the 0.05 level of significance.) Data from all patients who have received at least one dose of the drug or placebo will be analyzed. Thus, the analysis will be based on intention to treat. All tests will be two-sided, and conducted using a significance level of 0.05.

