The primary outcome is FEV₁ change from baseline. To test for a difference in the mean change between the treatment group and the control group, a two-sample t-test will be conducted. To estimate the difference in the mean change, the equivalent confidence interval procedure will be used. Prior to conducting the test, normality will be assessed for each group based on normal probability plots. If gross departures from normality are observed, a Wilcoxon rank sum test will be performed instead of the t-test. (With group sample sizes of 30, the t-test is fairly robust to departures from normality.)

The same analytical approach will be used to assess differences in the group means for the following variables: the primary outcome of change in respiratory symptom score, and the efficacy outcomes of change in density of colonization (per gram of sputum),

change in sputum cytokines and cell counts, and responses to all Likert-scale questions on the CFQ-R.

To analyze group differences in the efficacy outcome of time to next exacerbation, a time-to-event analysis will be conducted. Kaplan-Meier estimates will be obtained for each survival curve (where failure is defined by exacerbation). To compare the survival distributions, a log rank test will be employed.

To compare the proportion of subjects in each group who have experienced any adverse events, Fisher's exact test will be used. Since certain subjects may experience multiple adverse events, we will also compare the incidence of adverse events in each group. For this comparison, a test will be conducted to contrast the mean number of events in each group, where the two samples of event counts are treated as arising from independent Poisson distributions. To estimate the difference in group proportions and the difference in group means, equivalent confidence interval procedures will be employed.

The preceding inferential procedures will be conducted for individual types of adverse events (e.g., cough, chest tightness, headache), as well as the aggregate of all adverse events. Fisher's exact test will also be used to compare the compliance proportion and the proportion of rescue bronchodilator use in each group.

Since this study is a randomized, controlled clinical trial, we expect the treatment group and the control group to be balanced with respect to factors that could affect the primary

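### Compliance is tested only as a yes/no proportion with no stated cut-off, although doses taken per subject can be derived for most subjects and their mean would give a more powerful, cut-off-free comparison

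*Combined protocol and SAP*

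**What the plan says.** The analysis commitment is one sentence near the end of Outcomes: Fisher's exact test is to be "used to compare the compliance proportion and the proportion of rescue bronchodilator use in each group". The general rule for tests applies to it: "All tests will be two-sided, and conducted using a significance level of 0.05". The enrolment target is 60, "with a goal of 30 subjects in each group". No section defines a compliant subject, gives a cut-off, or plans an analysis of doses taken as a count or percentage.

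The data collected are richer than a yes/no:

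- Experimental Treatment sets the schedule as "Aerosolized 15% xylitol, 5 ml twice a day for 2 weeks". Control Treatment has the same frequency and duration.
- Administration: "All empty, unused and partially used study drug containers will be tracked by the investigators".
- Day 14 follow-up, for subjects discharged early: "They will be asked to keep a log of nebulizer use and bring back empty and unused vials on follow-up visit". That visit may fall on days 10 to 15. Subjects who do not attend are asked about compliance by phone.

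For quantitative outcomes, Outcomes already sets a rule: a two-sample t-test with its confidence interval, replaced by a Wilcoxon rank sum test if normality plots show gross departures. For adverse events it analyses both any/none and the number of events. Compliance gets only the yes/no form.

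**The concern.** A subject who took 27 of 28 doses and one who took 23 may fall in the same class, while two subjects who differ by one dose may fall in different classes. Where the line is drawn settles who counts as compliant. With no line in the plan, it could be drawn after the doses are known, in an unblinded trial. The test cannot be run as written without that unrecorded choice.

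The hypothesis in the Background is that xylitol will be safe and well tolerated, and ease of compliance is one stated reason for twice-daily dosing. Skipped or stopped doses are direct evidence on both. A comparison with low or cut-off-dependent power could show no difference where subjects on xylitol really took fewer doses.

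**Working it through.** **The plan's own figures.** No power is stated for compliance. The two figures nearby were checked first.

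- Log CFU, difference 1.5, SD 1.5: the normal approximation gives n = 2(1.96 + 0.84)² × (1.5/1.5)² = 15.7, so 16. The noncentral t gives 17 per group with power 0.807, as stated.
- Adverse events: 1 − 0.95³⁰ = 0.785, against the stated 80%.

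**Inputs from the documents.** 30 per arm, two-sided 0.05, and 2 × 14 = 28 scheduled doses per subject in each arm.

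**Assumed inputs.** Adherence rates, dose distribution and cut-offs, because the documents give none.

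**Step 1: Fisher on a per-subject yes/no, exact power at 30 v 30.**

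| Compliant, control v xylitol | Power |
|---|---|
| 90% v 80% | 0.10 |
| 90% v 70% | 0.37 |
| 90% v 60% | 0.71 |
| 80% v 60% | 0.30 |

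**Step 2: the same simulated subjects analysed both ways.** A subject is compliant if doses/28 reaches the cut-off.

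- *Graded skipping:* each subject has a dose-taking probability from a beta distribution with mean 0.90 (control) or 0.75 (xylitol) and concentration k, and doses are binomial out of 28. The intraclass correlation is 1/(k + 1): k = 6 gives 0.14, k = 3 gives 0.25.
- *Early stopping:* 5% v 35% of subjects stop in the first half, and the rest take nearly all doses.

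| Pattern | Welch t, mean doses | Wilcoxon | Fisher, 50% cut-off | Fisher, 80% | Fisher, 90% |
|---|---|---|---|---|---|
| Graded, 75% v 90% | 0.83–0.96 | 0.91–0.97 | 0.04–0.13 | 0.62–0.79 | 0.75–0.86 |
| Early stopping, 35% v 5% | about 0.85 | about 0.55 | 0.73 | 0.73–0.79 | 0.41–0.56 |

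The ranges in the graded row cover k = 3 and k = 6. The Fisher ranges in the early-stopping row come from separate runs. The 90% column is sensitive to how close to full dosing the continuing subjects are. At a 70% cut-off Fisher had 0.77 to 0.79 under early stopping.

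**Step 3: the loss against Welch, in power.**

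- Graded, 90% cut-off: 0.83 − 0.75 = 0.08 to 0.96 − 0.86 = 0.10.
- Graded, 80% cut-off: 0.96 − 0.79 = 0.17 to 0.83 − 0.62 = 0.21.
- Graded, 50% cut-off: 0.83 − 0.13 = 0.70 to 0.96 − 0.04 = 0.92.
- Early stopping, cut-offs 50% to 80%: 0.85 − 0.79 = 0.06 to 0.85 − 0.73 = 0.12.
- Early stopping, 90% cut-off: 0.85 − 0.56 = 0.29 to 0.85 − 0.41 = 0.44.

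No single cut-off is safe: 90% costs least under graded skipping and most under early stopping. Welch was above Fisher at every cut-off tried in both patterns, and in a smaller graded gap (means 25.2 v 22.4 doses: Welch 0.81–0.82, Fisher 0.53 at 80% and 0.61 at 90%). With equal arms its rejection rate was 0.03 to 0.05.

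**Step 4: the denominator.** A subject seen on day 10 can have been scheduled for at most 2 × 10 = 20 doses. Scored out of 28, perfect adherence would read 20/28 = 71%, below an 80% cut-off.

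**The case against.** The strongest reply is that this is a definition gap in an ancillary comparison, and that the power argument depends on the pattern assumed. Much of that stands.

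- A reader might infer that Fisher's test throws away much of the power whatever happens. The documents do not support this. They give no adherence rates, and the rule that ends study drug after a 20% FEV₁ fall can produce all-or-nothing exposure. In that pattern Fisher at a 70% or 80% cut-off is only modestly below Welch and clearly above Wilcoxon.
- A reader might therefore send compliance to the plan's existing t-test/Wilcoxon rule. Counts capped at 28 with a low cluster of stoppers could well trigger the switch to Wilcoxon, which would then have less power (about 0.55) than Fisher at most cut-offs.
- A reader might take the compliance proportion to mean doses pooled over subjects, 30 × 28 = 840 per arm. Fisher's test would then ignore clustering, and its false-positive rate would be 36% to 47% in simulations with equal 85% adherence. But Outcomes introduces Fisher's test for the proportion of subjects, and the sentence pairs compliance with rescue use. The natural reading is subjects.
- A reader might infer that the trial's tolerability conclusion is at risk. Endpoints does not list compliance among the safety assessments. FEV₁, withdrawal, rescue use, adverse events and symptom scores carry that conclusion, and Study Performance tracks terminations with reasons.
- Nor can every subject be assumed to have a vial count out of 28: some have phone information only, and visits may be early.

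The reply does not remove the core. The cut-off is absent, it can change the result in either pattern, and a comparison that needs no cut-off did better at every cut-off tried.

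**Conclusion.** The concern holds as a minor point about one ancillary tolerability comparison. Two parts rest on the text alone: the cut-off is missing, and no planned analysis uses doses taken. The size of the power loss rests on assumed adherence patterns with 30 per arm. It runs from under 0.10 where the cut-off happens to suit the pattern to 0.70 or more where few subjects fall below it. The advantage claimed is for the difference in mean doses, not for any rank test or for quantitative analysis in general. The primary FEV₁ analysis and the main safety comparisons are unaffected.

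**What to change.** Replace the compliance part of the Fisher sentence in Outcomes with a short paragraph that does the following:

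1. Define compliance per subject as doses taken divided by doses scheduled up to the day-14 visit: 28, or fewer if the visit falls earlier within days 10 to 15. Count doses after a stop of study drug as not taken.
2. Compare arms by the difference in mean percentage of doses taken, with a Welch t or bootstrap confidence interval, and exempt this variable from the switch to Wilcoxon.
3. For subjects who do not return, use the count reported by phone, and repeat the analysis without them as a sensitivity analysis.
4. Keep any yes/no summary descriptive, with its cut-off written down before the data are seen.

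The data are already planned, except that the phone contact must ask for a dose count. The cost is a few sentences and a little more analysis. The remaining weakness is that phone-reported counts are less precise than vial counts.

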Endpoints: Primary outcome will be FEV₁ change from baseline. Other safety assessments include vital signs within 30 minutes after nebulization, withdrawal from the study, rescue bronchodilator use, incidence of treatment related adverse events, and laboratory tests (chemistry and liver function tests). Efficacy outcomes include difference in density of colonization per gram of sputum from baseline to day 14, time to next hospitalization, difference in CFQ-R, sputum cytokine levels and cell counts.

Adverse events such as cough, chest tightness, and headache will be scored on a visual analog scale. Other variables collected include antibiotic and other medication use during the hospitalization, demographics, organ involvement with CF, genotype data from medical records. Follow-up phone calls will be made 1 week, 3 months and 6 months

after study completion for any complications and to assess the time to next hospitalization.

Adverse events: Any untoward medical occurrence (abnormal symptom, sign or laboratory value) in a study subject that is temporally associated with the study drug will be reported as an adverse event. The event does not have to have a causal relationship with the treatment. The event will be classified by the investigator as mild, moderate or severe. The relationship of an adverse event to the study drug will be determined by the investigator to be ‘unlikely to be related, possibly related, probably related or definitely related’.

Future Use of Stored Specimens

Subjects will be asked for permission to keep any remaining unlinked sputum and blood specimens for possible use in future research studies. Samples may be shared with other investigators at other institutions. The samples will not be sold or used directly for production of any commercial product. No human genetic tests will be performed on samples. Each sample will be labeled only with a study ID to protect subject’s confidentiality.

There are no benefits to subjects in the future research use of their specimens. Reports about future research done with these samples will not be kept in their health records.

Subjects can decide if they want their samples to be used for future research or have their samples destroyed at the end of the study. A subject’s decision can be changed at any time prior to the end of the study by notifying the study investigators in writing.

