and efficacy outcomes, such as age and gender. For such variables, descriptive statistics will be compiled for each group to ensure that the randomization has been effective. If a marked difference is observed in the distribution of any variables, an analytical approach will be utilized that will allow us to control for these variables. Specifically, the t-test can be replaced with an analysis of covariance model, the log-rank test can be replaced with a Cox proportional hazards model, Fisher's exact test can be replaced with a logistic regression model, and the two-sample Poisson test can be replaced with a Poisson regression model.

All analyses will be performed by the study statistician using SAS version 9.2 (SAS Institute, NC).

Risks: Exposure to xylitol and hypertonic saline is expected to not elicit any significant symptoms other than some cough; however we recognize that there may be a possibility of bronchospasm with the hyperosmolar xylitol in a subgroup of subjects with CF who have bronchial hyperresponsiveness that was not known previously.

Blood draw and spirometry are a part of standard care and will not pose added risks.

With the admission labs that are routinely done, we will collect another red top tube for liver function tests if they were not planned. Answering questions may involve some concentration and may be boring.

Risks are minimized as follows: In the event of bronchospasm with the study drug, immediate treatment with bronchodilators is available. The subject will undergo a spirometry and if the FEV₁ has declined by 20%, the subject will be terminated from the

study. Blood draw will be performed by trained nurses or the hospital IV team with minimal discomfort. Spirometry will be done by experienced respiratory therapists. Symptom questionnaire will be administered by well-trained interviewers and will be as brief as possible.

Confidentiality: All the test results and questionnaire will be stored in the research office under lock and key with access only to the investigators. Once all testing is complete and data is entered for analysis, there will be no identifiers connecting the subject to the data. All results will be reported in summary without identifying the subjects. Blood and urine specimens will not be stored for future use.

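### After a 20% FEV₁ fall with bronchospasm, one section keeps the subject in the study and another terminates the subject; the first-dose rule also ends follow-up of randomized, dosed subjects

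*Combined protocol and SAP*

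**What the plan says.** Five places in the protocol deal with a 20% fall in FEV₁.

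- *Risks are minimized as follows*, on bronchospasm with the study drug: "bronchodilators is available. The subject will undergo a spirometry and if the FEV₁ has declined by 20%, the subject will be terminated". The sentence ends by naming the study as what the subject is terminated from.
- *Statistical analysis, Study Performance*: if FEV₁ "has declined by 20%, the subject will be terminated from the study". No bronchospasm or other trigger is named here.
- *In the event of bronchospasm*: after a fall of 20% or more the subject gets no further drug, but "they will remain in the study for completion of data collection".
- *First dose pre and post spirometry*: "Subject is excluded from the study if SpO₂ is <89% or FEV₁ declines by 20% or greater from baseline".
- *Stopping criteria*: a 20% drop in FEV₁ % predicted stops further exposures. Whether the subject stays in the study is not stated.

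Three other provisions bear on the consequence. *Screening and Baseline Visit* fixes the order of events: "Once consented, subjects will be randomized to either xylitol or saline group", with treatment starting the day after admission. *Outcomes* defines the analysis set: "Data from all patients who have received at least one dose of the drug or placebo will be analyzed", described as intention to treat. Leaving the study is itself reported. *Endpoints* lists among the safety assessments "vital signs within 30 minutes after nebulization, withdrawal from the study, rescue bronchodilator use", and *Study Performance* adds: "The number of study terminations and reason for termination will be measured".

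**The concern.** The trial is about safety, its primary outcome is FEV₁ change, and the Risks section names bronchospasm as the recognized hazard of hyperosmolar xylitol. The subjects affected by these rules are therefore the ones whose later course matters most.

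Two things are at stake. First, staff and the study statistician can apply different rules to the same subject, and the reported withdrawals and terminations by arm then depend on which rule was used. Second, if a subject leaves under the termination or first-dose wording, the Day 14 spirometry, sputum, CFQ-R and blood tests, and the later phone calls about exacerbations, admissions and adverse events, may be missing. They would be missing because of a fall in the primary outcome or a safety reaction, not by chance. The plan gives no rule for handling such missing values.

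**Working it through.** The point rests on reading the text side by side. The arithmetic only shows scale.

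**1. The rules compared**

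| Section | Trigger | Fall measured as | Drug | Subject |
|---|---|---|---|---|
| In the event of bronchospasm | Bronchospasm | 20% or more from baseline | Stopped | Stays for data collection |
| Risks are minimized as follows | Bronchospasm on study drug | 20%, no reference given | Not stated separately | Terminated |
| Study Performance | None stated | 20%, no reference given | Not stated separately | Terminated |
| First dose pre and post spirometry | Check after first dose | 20% or more from baseline (best FEV₁ × 0.80), or SpO₂ <89% | Not stated separately | Excluded from the study |
| Stopping criteria | Any subject | 20% in FEV₁ % predicted | Exposures stop | Not stated |

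The first two rows share the trigger and the 20% threshold but give opposite dispositions. The last row fits either, so it does not settle the matter.

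**2. Order of events for the first-dose rule.** Randomization follows consent on the day of admission, dosing starts the next day, and the check follows the dose. Everyone who fails the check is randomized and dosed, and so belongs to the analysis set in *Outcomes*.

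**3. Follow-up exposed.** One Day 14 visit plus three phone calls (week 1, Day 90, Day 180) is 1 + 3 = 4 contacts per subject. For 1, 2 or 3 subjects that is 4, 8 or 12.

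**4. Termination count.** With k bronchospasm fallers in an arm of 30, the termination wording gives k/30 = 3.3%, 6.7% or 10.0% for k = 1, 2, 3. The retention wording gives 0% for each. The values of k are illustrative.

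**5. Chance that the question arises.** The documents give no fall rate, so p is assumed. P(at least one) = 1 − (1 − p)ⁿ.

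| Assumed p | n = 30 | n = 60 |
|---|---|---|
| 1% | 26.0% | 45.3% |
| 2% | 45.5% | 70.2% |
| 5% | 78.5% | 95.4% |
| 10% | 95.8% | 99.8% |

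The 5% row borrows the plan's planning rate for an adverse event. At n = 30 it is the same calculation as the plan's own 80% detection figure.

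**6. Possible effect on a mean change, if fallers' later values are missing.** Error in the observed arm mean = (k/30) × (mean of the rest − mean of the fallers). Assume the fallers' unseen Day 14 change lies between 10 points of % predicted below and 10 above the rest:

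- k = 1: (1/30) × (±10) = ±0.33 points
- k = 2: (2/30) × (±10) = ±0.67 points
- no gap: 0

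The standard error of the difference between arms is SD × √(2/30), which is 1.29, 2.58 or 3.87 for an assumed SD of 5, 10 or 15. The largest error, 0.67, is then 0.52, 0.26 or 0.17 standard errors.

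**7. Definition of the fall.** For a subject at 50% predicted, a relative fall of 20% means 0.80 × 50 = 40, a loss of 10 points. If the *Stopping criteria* wording is read as 20 points of % predicted, the subject must reach 30, a relative fall of 20/50 = 40%. The two readings identify different subjects.

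**The case against.** The contradiction over bronchospasm cannot be argued away, but several limits on it are fair.

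- **The first-dose rule and the analysis set.** A reader might infer that the first-dose rule contradicts the analysis-set statement. It does not. It excludes from the study and says nothing about the analysis, and the pre- and post-dose FEV₁ and SpO₂ of these subjects exist and can be analyzed. What stands is outcome-dependent loss of follow-up with no stated handling.
- **Direction of bias.** A reader might infer that removing fallers makes xylitol look safer by several points. That would require an acute fall, treated with bronchodilators, to persist unchanged to Day 14. It would also require treating a 20% relative fall as 20 points. The documents support neither step.
- **Study Performance.** Its sentence has no trigger and matches the one in the Risks section, so it may be a repeat rather than an independent rule. It is secondary support only.
- **Counts.** The reason for each termination is to be recorded, so terminated fallers would remain identifiable. *Endpoints* does not say whether withdrawal includes termination by the investigator. This softens the ambiguity but does not remove it.
- **Likelihood.** The probabilities in step 5 rest on borrowed or assumed rates. They count any faller, while the direct conflict concerns only those with bronchospasm.
- **Safety information under either rule.** The drug stops, the fall is still an adverse event, and the three-subject stopping rule can still count it.
- **The DSMP.** *Safety Monitoring* refers to a DSMP that is not among the documents. It may say which rule governs, but the protocol text would still conflict.

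**Conclusion.** The point holds and should be fixed. For bronchospasm on study drug with a 20% FEV₁ fall, the protocol both keeps the subject for data collection and terminates the subject. This needs no assumption. Separately, the first-dose rule ends study follow-up for randomized, dosed subjects because of a fall in the primary outcome or a low SpO₂, although they remain in the analysis set.

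What can be sized from the documents is 1 of 30 (3.3 percentage points) in an arm's termination count per bronchospasm faller, and up to four lost contacts per subject removed. The frequency is not given. The size and sign of any bias in mean FEV₁ change are unknown, and the bias may be zero. Under the assumptions in step 6 it is at most 0.67 points in either direction.

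A reader might also notice that no time point is named for the primary FEV₁ change. That is a separate design choice for the sponsor and not part of this point.

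**What to change.** Apply the plan's own bronchospasm rule everywhere. In *First dose pre and post spirometry*, *Study Performance* and *Risks are minimized as follows*, replace exclusion or termination from the study with wording to this effect: study drug is stopped; the subject stays in the study for the Day 14 assessments and phone follow-up and is included in the analysis.

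Define the fall once, as a relative fall of 20% or more from baseline FEV₁, and use that definition in every section, including *Stopping criteria*. Keep SpO₂ below 89% as an additional reason to stop drug at the first dose. Report these subjects as study drug discontinued, by arm, separately from withdrawal from the study.

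The cost is a few clauses of text and up to four already scheduled contacts per subject. That is 4 to 12 contacts for 1 to 3 subjects, or 24 if 10% of 60 (6 subjects) were affected. No more patients and no more drug exposure are needed. Subjects may still decline follow-up, and those who do would count as withdrawals.
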